| IP Administration                                      |                  |                           | ×    |                   |                       |                 |                 |                 |                 |                       | X                            | X                            | X                            |                 |                        |                        |                           |

## CONFIDENTIAL Page 17

| MULTIPLE ASCENDING DOSE COHORT S | COHORT SCHI    | SCHEDULE OF ASSESSMENTS   | ASS | ESSM      | ENTS                  |           |           |          | •        |                       | •                     | •                                 |                             | •         | •                      |   |                           |
|----------------------------------|----------------|---------------------------|-----|-----------|-----------------------|-----------|-----------|----------|----------|-----------------------|-----------------------|-----------------------------------|-----------------------------|-----------|------------------------|---|---------------------------|
| VISIT NAME                       | SCREENING      |                           |     |           | DAY
1 K | *         |           |          |          | DAY
2 A | DAY
8 K | DAY 1                             | DAY
22 K      | DAY
29 | DAY
50 A | $\begin{array}{c ccccccccccccccccccccccccccccccccccc$ | DAY
180 M , |
| VISIT NUMBER                     | $1^{I}$        |                           |     |           | 2                     |           |           |          |          | 3                     | 4                     | S.                                | 9                           | 7         | ∞               | 6   | 10                        |
| TIME POST FIRST DOSE             | NA             | PRE-
DOSE J | 0   | 15
MIN | 30
MIN             | 09
MIN | 90
MIN | 2
HRS | 4
HRS |                       |                       |                                   |                             |           |                        |   |                           |
| ALLOWABLE VISIT WINDOW           | -28 to -1 days |                           |     | -/- 2     | +/ <del>-</del>       | -/-       | -/+       | -/+      | -/+      |                       | -
1                | + 1                               | - <del>-</del>              | +/-       | + %                    | -/+   | 30                        |
|                                  | ,              |                           |     | Min       | Min                   | Min       | Min       | Min      | Min      |                       | Day L I    | Day L Day L | $\mathrm{Day}^{\mathrm{L}}$ | Day       | Days                   | Days  | Days                      |
| Adverse Events H      |                |                           | X   | X         | X                     | X         | X         | X        | ×        | X                     | X                     | X                                 | ×                           | X         | X                      | ×   | X                         |
| Contraception Review             | X              |                           |     |           |                       |           |           |          | X        | X                     | X                     | X                                 | X                           | X         |                        |   |                           |

A Day 2 and Day 50 Visits may be conducted via telephone

B Vital signs (temperature, seated blood pressure, and pulse rate) should be collected pre-dose and 30 minutes after dosing on Days 8, 15, and 22

C Tibial-femoral x-rays to confirm the diagnosis of OA and Kellgren & Lawrence Grade must be of acceptable quality and acquired within 6 months prior to Screening

D Safety laboratory testing includes hematology, chemistry, and urinalysis; will be performed at the site's laboratory

E For female subjects; will be performed at the site's laboratory

F The WOMAC should be administered at the beginning of the visit prior to completing other procedures

G Optional banked biospecimen collection

H Adverse Events are captured starting at time of consent. Any Adverse Events during Screening and Day 1 will be captured and noted as part of medical history

Screening procedures may be completed across multiple days during the 28 day screening period and do not need to be conducted on consecutive days

J All D1 predose laboratory assessments should be conducted within 48 hours prior to IP administration and other pre-dose assessments conducted within 2 hours prior to IP administration

K Subjects may be discharged after at least 2 hours of safety observation following the last procedure

L There should be minimum of 7 days between the IA injections

M Procedures may be split into 2 days to allow for the completion of multiple procedures

N Assessments that do not require a visit such as review of concomitant medications for Day 180 may be done remotely via phone call, text message, email. PE can be conducted by telemedicine. Laboratory assessment can be done at laboratories other the clinical sites

#### 1. INTRODUCTION

Osteoarthritis (OA) is a highly prevalent, degenerative joint disease that involves the articular cartilage and subchondral bone in addition to the surrounding tissues (Litwic, et al., 2013). OA is characterized by the progressive degeneration of articular cartilage, in part due to abnormal activation, differentiation, and death of articular chondrocytes, the primary cell type present in cartilage (Goldring & Goldring, 2010). OA is the most common joint disorder in the United States, affecting at least 27 million Americans (Zhang & Jordan, 2010). The joints most often affected by OA are the hands, knees, hips, and spine. The primary symptoms of OA are joint pain, stiffness, and movement limitations. OA may have a profound effect on quality of life, impacting both the physical function and psychological well-being of patients.

Current treatment options for OA include pharmacological and non-pharmacological interventions focused primarily on reducing pain and improving physical function. Surgical intervention to replace the hip, knee, or shoulder joint is required for an increasing number of patients who do not have adequate pain relief or preservation of function following more conservative treatment options. There are no approved disease modifying treatments that delay or prevent OA progression or joint destruction (Hunter, 2011).

Since the hallmark of OA is cartilage loss leading to joint destruction, a potential approach to treating OA is stimulation of chondrocyte regeneration from endogenous mesenchymal stem/progenitor cells in the cartilage. KA34 is an experimental compound that exhibits chondrogenic activity both *in vitro* and in animal models of OA.

#### 1.1. Mechanism of Action/Indication

KA34 is a first-in-class, low molecular weight, drug-like molecule which promotes articular cartilage repair and is being explored as a potential treatment for osteoarthritis of the knee.

#### 1.2. Background

Osteoarthritis (OA) is a highly prevalent disease characterized by progressive degeneration of the articular cartilage (Litwic, et al., 2013). The prevalence of symptomatic OA increases with age and BMI. Symptomatic OA of the knee occurs in approximately 10% of men and 13% of women aged 60 years or older in the United States (Zhang & Jordan, 2010).

OA is generally classified as idiopathic, with no identifiable cause, or secondary. Secondary OA is related to a known medical condition or event, such as trauma, congenital or developmental disease, calcium deposition disease, or another bone and joint disorder such as rheumatoid arthritis. Idiopathic OA can impact the hands, feet, knees, hips, spine, or other joints such as the shoulders, ankles, or wrists. Idiopathic OA is considered generalized if it impacts three or more types of joints (Altman, et al., 1986).

OA is diagnosed based on clinical examination, laboratory test results, and radiographic findings. Developing a sensitive, specific classification system for OA is challenging due to the non-specific nature of the symptoms and the lack of a definitive diagnostic test. Radiography can detect changes in articular cartilage and tissue reaction around the joint, but

radiographs are not sufficient to diagnose OA as 40% of patients with radiographic changes consistent with OA do not have clinical symptoms (Altman, et al., 1986).

The widely used American College of Rheumatology (ACR) criteria for knee OA require the presence of knee pain in combination with other signs or symptoms, radiographic changes, or laboratory findings and provide a series of algorithms (decision trees) that support the classification of OA (Altman, et al., 1986). The severity of knee OA is generally graded using the Kellgren and Lawrence radiological classification system (Kellgren & Lawrence, 1957).

#### 1.2.1. Pharmacology and Pharmacokinetics

KA34 was investigated in *in vitro* and *in vivo* pharmacodynamic studies. KA34 effectively induces human mesenchymal stem cell (MSC) differentiation into chondrocytes *in vitro* and improves osteoarthritic outcomes in animal models of OA.

In vitro primary pharmacodynamic studies demonstrated that KA34 can induce a two-to four-fold increase in mRNA expression of the chondrogenic genes sex-determining region Y-Box 9 (SOX9), proteoglycan 4 (PRG4), and cartilage-oligo matrix protein (COMP). KA34 at 1  $\mu$ M had no off-target inhibition or stimulation higher than 50% in receptor binding, enzyme and uptake assays.

KA34 was investigated in multiple *in vivo* primary pharmacodynamic studies in both rat and dog models of OA. KA34 treatment improved osteoarthritic outcomes in both rat and canine models of OA. Reductions in cartilage degeneration and cartilage depth ratios occurred at doses of 1 µg and 35 µg per knee in rat and dog, respectively, when KA34 was administered IA either once weekly or once every other week. Normalizing these putative efficacious doses by using rat, dog, and human synovial knee volume, the predicted human efficacious dose is approximately 200 µg per knee. KA34 treatment also significantly increased the plasma biomarker PIINP in the dog which is consistent with induction of cartilage regeneration, the hypothesized mechanism of action.

Pharmacokinetic data for KA34 were obtained from specific pharmacokinetic studies and from adjunct toxicokinetic studies included with toxicology evaluations. The overall range of IA doses explored was 2.1  $\mu$ g – 12  $\mu$ g per rat knee and 35  $\mu$ g – 100  $\mu$ g per dog knee. The overall range of IV doses explored was 0.2 – 2.5 mg/kg in the rat and 0.125-1.25 mg/kg in the dog.

Upon intra-articular injection, KA34 exhibits low plasma levels and rapid clearance in preclinical species. A single IA dose of KA34 at 2.11 µg per rat knee resulted in an AUC0- $\tau$  of 12.1 ng\*h/mL and a Cmax of 13.8 ng/mL. In a five-week rat IV dose study at 2.5 mg/kg/week KA34 (NOAEL), the Study Day 1 average AUC0- $\tau$  was 2915 ng\*h/mL and the average Cmax was 5930 ng/mL. Therefore, the rat IV/IA AUC exposure margin was 240-fold and the Cmax exposure margin was 429-fold. A similar comparison in dogs given a study day one single IA dose of 35 µg/knee (efficacious dose) versus an IV NOEL dose of 1.25 mg/kg resulted in dog IV/IA AUC exposure margin of 453-fold and the Cmax exposure margin of 1123-fold.

KA34 had no effects on central and peripheral nervous system activities or measured respiratory parameters. In an IV conscious, telemetered, cardiovascular dog study, a

transient decrease in systolic blood pressure (14 and 15 mmHg) was noted at 0.5 hours after treatment at doses of 0.600 and 1.250 mg/kg, respectively. These minimal blood pressure changes occurred at much higher exposure levels than are anticipated via IA injection. Vital signs, including seated blood pressure, will be monitored before and after dosing in this study.

Additional information about KA34 may be found in the Investigator's Brochure (IB).

#### 1.2.2. Toxicology

A nonclinical toxicology program was conducted to support the administration of KA34 in this first in human clinical trial. The Sprague-Dawley rat and Beagle dog were selected as the relevant nonclinical species due to a similar *in vitro* metabolite profile compared to human.

The KA34 toxicology program consisted of: single dose IA and IV non-GLP toxicity studies in the rat and dog, 5-week IA and IV repeat dose toxicity GLP studies in the rat and dog with a 14-day recovery period, and a battery of *in vitro* and *in vivo* GLP genotoxicity studies.

In the single dose IA (femoro-tibial joint) toxicity studies, KA34 was well tolerated up to 12  $\mu$ g per rat and 200  $\mu$ g per dog. In the single dose IV toxicity studies, KA34 was well tolerated up to 2.4 mg/kg in rats and 1.2 mg/kg in dogs.

In the 5-week rat IA toxicity study, the no-observed-effect-level (NOEL) was determined to be  $6\mu g/rat/week$ . In the 5-week rat IV toxicity study, the no-observed-adverse-effect-level (NOAEL) was determined to be 2.5 mg/kg/week. In the 5-week dog IA toxicity study, the NOEL was determined to be 100  $\mu g/dog/week$ . In the 5-week dog IV toxicity study, the NOAEL was determined to be 1.25 mg/kg/week.

KA34 was not genotoxic in *in vitro* bacterial mutation and mammalian micronucleus tests or in the *in vivo* rat micronucleus assay.

Additional information about KA34 may be found in the Investigator's Brochure (IB).

#### 1.3. Rationale

#### 1.3.1. Study Rationale

KA34 is being investigated as a potential treatment for patients suffering from OA. Treatments with KA34 improves osteoarthritic outcomes in rat and dog models of OA. KA34 was safe and well tolerated when administered IA and IV in GLP toxicology studies in rats and dogs. This first in human study will evaluate the safety and tolerability of KA34 in subjects with OA of the knee. The study will also allow for pharmacokinetic and pharmocodynamic assessment of KA34 in this patient population to inform future development plans. KA34 will be administered via intra-articular injection to minimize systemic exposure.

#### 1.3.2. Dose Rationale

This selection of doses for this first in human study was based on the relevant preclinical data. The initial cohorts treated in the study will receive single-ascending doses of KA34. Once the safety and tolerability of single doses of KA34 have been established, additional cohorts will receive multiple ascending doses of KA34.

The dog was selected as the most sensitive species based on a lower local safety margin, lower human equivalent dose (HED), and lower systemic exposure compared to the rat. The HED was determined based on the no observed effect level (NOEL) from the 5-week dog IA toxicity study. The 100  $\mu$ g/knee/week NOEL in dogs was normalized by synovial volume and injected concentrations of KA34 in the knee. The synovial knee volume used in the calculation was 1.2 mL for the dog and 7 mL for human (Kraus, et al., 2007) (Wehr, et al., 2007). The NOEL 100  $\mu$ g concentration normalized in the dog was 83.3  $\mu$ g/mL and 583  $\mu$ g/knee in humans. Based on a 3X safety margin and the lack of any remarkable findings at the high dose from the 5-week IA and IV toxicity studies in dog and rat, the initial clinical maximum recommended starting dose (MRSD) was calculated as 194  $\mu$ g/knee. However, the KA34 concentration analysis of the 200  $\mu$ g/mL/week formulation used during Week 5 of the five-week dog IA repeat toxicity study was found to be below the nominal concentration, up to -26% of nominal in dogs. Therefore, a modified MRSD of 143  $\mu$ g/knee (74% of the 194  $\mu$ g/knee) was calculated.

The starting dose in humans selected for the single ascending dose portion of the study is 50  $\mu$ g, approximately 1/3 of the MRSD and 1/12 of the NOEL. The starting dose selected for the multiple ascending dose portion of the study is 100  $\mu$ g, which is approximately 1/6 of the NOEL.

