#### STUDY DESIGN

This is a randomized, double-blind, placebo-controlled study to assess the safety, tolerability, pharmacokinetics, and pharmacodynamics of KA34 when administered via intra-articular injection to subjects with osteoarthritis of the knee. All subjects will receive a 5 mL injection of KA34 or placebo in the affected knee.

The study will consist of approximately 7 cohorts of subjects who will be randomized to receive KA34 or placebo. KA34 will be provided as a solution with a concentration of 200 µg per mL.

KA34 will be administered as a single dose to the following cohorts:

| DOSE            | N PER COHORT               |
|-----------------|----------------------------|
| 50 μg per knee  | 4 (3 – Active & 1 Placebo) |
| 100 μg per knee | 4 (3 – Active & 1 Placebo) |
| 200 μg per knee | 8 (6 – Active & 2 Placebo) |
| 400 μg per knee | 8 (6 – Active & 2 Placebo) |

The decision to escalate to the next dose cohort will be made by the sponsor, based on the recommendation of the Data Safety Monitoring Board (DSMB), following a (blinded) review of all available safety information from Day 8 post-dose of the preceding dose cohort. (see section 9.7, DSMB)

Once the safety and tolerability of single doses of KA34 have been assessed, multiple-dose administration of KA34 will be evaluated. The multiple-dose portion of the study will be initiated after a thorough review of the Day 29 safety data from the single-dose cohorts. During the multiple dose portion of the study, KA34 will be administered as 4 weekly doses to the following cohorts:

| DOSE                          | N PER COHORT                |
|-------------------------------|-----------------------------|
| 100 μg per knee per injection | 12 (9 – Active & 3 Placebo) |
| 200 μg per knee per injection | 12 (9 – Active & 3 Placebo) |
| 400 μg per knee per injection | 12 (9 – Active & 3 Placebo) |

The doses administered to subsequent cohorts in either the single or multiple dose portions of the study may be lowered if any safety or tolerability issues are identified which suggest that the planned doses may pose a risk to study participants. Additional dose groups may be added to the study depending on the observed safety and tolerability profile of KA34 or if the pharmacokinetic data permit a higher than anticipated dose while remaining within a safe exposure limit based on the toxicokinetics and safety profile from the nonclinical toxicology studies.

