#### 3. STUDY DESIGN

#### 3.1. Study Overview

This is a randomized, double-blind, placebo-controlled study to assess the safety, tolerability, pharmacokinetics, and pharmacodynamics of KA34 when administered via intra-articular injection to subjects with osteoarthritis of the knee. All subjects will receive a 5 mL injection of KA34 or placebo in the affected knee.

The study will consist of approximately 7 cohorts of subjects who will be randomized to receive KA34 or placebo. KA34 will be provided as a solution with a concentration of 200 µg per mL.

KA34 will be administered as a single dose to the following cohorts:

| DOSE            | N PER COHORT               |
|-----------------|----------------------------|
| 50 μg per knee  | 4 (3 – Active & 1 Placebo) |
| 100 μg per knee | 4 (3 – Active & 1 Placebo) |
| 200 μg per knee | 8 (6 – Active & 2 Placebo) |
| 400 μg per knee | 8 (6 – Active & 2 Placebo) |

Once the safety and tolerability of single doses of KA34 have been assessed, multiple-dose administration of KA34 will be evaluated. The multiple-dose portion of the study will be initiated after a thorough review of the safety data from the single-dose cohorts. During the multiple dose portion of the study, KA34 will be administered as 4 weekly doses to the following cohorts:

| DOSE                          | N PER COHORT                |
|-------------------------------|-----------------------------|
| 100 μg per knee per injection | 12 (9 – Active & 3 Placebo) |
| 200 μg per knee per injection | 12 (9 – Active & 3 Placebo) |
| 400 μg per knee per injection | 12 (9 – Active & 3 Placebo) |

The doses administered to subsequent cohorts in either the single or multiple dose portions of the study may be lowered if any safety or tolerability issues are identified which suggest that the planned doses may pose a risk to study participants. Additional dose groups may be added to the study depending on the observed safety and tolerability profile of KA34 or if the pharmacokinetic data permit a higher than anticipated dose while remaining within a safe exposure limit based on the toxicokinetics and safety profile from the nonclinical toxicology studies.

The study will be conducted at approximately 4 sites in the United States. Approximately 60 subjects will be randomized to participate in this trial.

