#### 3.2. Dose Escalation

The decision to escalate to the next dose cohort of the study will be made by the sponsor, based on the recommendation of the Data Safety Monitoring Board (DSMB) following a (blinded) review of all available safety information from Day 8 post-dose of the preceding dose cohort in the single dose portion of the study(see Section 9.7, DSMB) The decision to initiate the multiple dose portion of the study will be made by the sponsor, after all cohorts have completed dosing in the single ascending dose portion of the study and based on the recommendation by the DSMB following a (blinded) review of all available safety information from Day 29.

The decision to escalate to the next dose cohort in the multiple dose portion of the study will be made by the sponsor based on the recommendation of the DSMB following a (blinded) review of the available safety data from Day 8 post-dose, after all subjects have been dosed in the preceding dose cohort. The safety information considered during this review will include adverse events, changes in vital sign measurements, clinical laboratory test values, and ECG results. Dose escalation will be stopped if it is determined that the limits of safety or tolerability have been reached; this decision will be made following the recommendation by the DSMB.

The doses administered to subsequent cohorts in either the single or multiple dose portions of the study may be lowered if any safety or tolerability issues are identified which suggest that the planned doses may pose a risk to study participants. Additional dose groups may be added to the study depending on the observed safety and tolerability profile of KA34.

Dose escalation will be paused if any of the following occur:

- 50% or more of the subjects at a given dose level develop similar clinically significant laboratory, ECG, or vital sign abnormalities or severe adverse events (AEs) in the same organ class, indicating dose-limiting intolerance
- A serious adverse event (SAE) that is deemed causally related to KA34 by the DSMB
- Additional safety data from a dose cohort are required to determine whether the limit of safety or tolerability has been reached
- Any other safety findings that, at the discretion of the DSMB, indicate that dose escalation should be halted

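### Do the unnumbered exposure limit for added dose groups, and the mix of a reduced MRSD with an unreduced NOEL, call for a change?

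*Protocol*

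**What the plan says.** **Dose rationale (Protocol 1.3.2).** The dog 5-week intra-articular NOEL of 100 µg per knee per week is scaled by synovial volume to 583 µg per human knee. Dividing by 3 gives an MRSD of 194 µg. The Week 5 dog formulation "was found to be below the nominal concentration, up to -26% of nominal in dogs", so the MRSD is lowered to 74% of 194, printed as 143 µg. The 50 µg single-dose start is then placed at "approximately 1/3 of the MRSD and 1/12 of the NOEL", and the 100 µg multiple-dose start at a level "which is approximately 1/6 of the NOEL".

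**Added dose groups.** The protocol summary (Study Design), Protocol 3.1 and SAP 3.1 carry the same clause with two routes joined by *or*. One is the observed safety and tolerability of KA34. The other applies "if the pharmacokinetic data permit a higher than anticipated dose while remaining within a safe exposure limit", and Protocol 3.1 draws that limit from the nonclinical work: "while remaining within a safe exposure limit based on the toxicokinetics and safety profile from the nonclinical toxicology studies". No value or unit is given. Protocol 3.2 states only the first route: "Additional dose groups may be added to the study depending on the observed safety and tolerability profile of KA34".

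**Nonclinical margins.** Protocol 1.2.1 compares a 35 µg intra-articular dose in the dog "versus an IV NOEL dose of 1.25 mg/kg resulted in dog IV/IA AUC exposure margin of 453-fold". Protocol 1.3.2 explains the choice of species: "The dog was selected as the most sensitive species based on a lower local safety margin", among other reasons.

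**The concern.** Three things catch the eye.

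1. The MRSD is the NOEL divided by 3. If the formulation finding justifies cutting one, the other would be expected to move with it. Instead, one sentence compares 50 µg with a cut MRSD and an uncut NOEL, without saying so.
2. The section that governs escalation (3.2) allows added dose groups with no stated limit. Section 3.1 names a limit but gives no figure.
3. The limit is worded in terms of pharmacokinetics and exposure. In the dog, plasma margins are far wider than the margin in the joint, so a plasma limit might not restrain the dose in the knee.

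If 583 µg were the effective ceiling, the basis would matter at the top planned dose of 400 µg. The NOEL would be 1.46 times that dose as printed, but only 1.08 times if the full shortfall applied throughout the dog study. In a first-in-human trial, an unclear limit on added cohorts deserves a check.

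**Working it through.** **Inputs** (Protocol 1.2.1, 1.3.2 and 3.1): dog NOEL 100 µg; synovial volumes 1.2 mL (dog) and 7 mL (human); safety factor 3; shortfall up to 26%; starting doses 50 and 100 µg; top planned dose 400 µg; dog efficacious dose 35 µg; dog AUC margin 453-fold.

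**Step 1. Reproduce the printed figures.**
- Concentration: 100 / 1.2 = 83.3 µg/mL.
- Human-equivalent NOEL: 83.3 × 7 = 583 µg per knee.
- MRSD: 583 / 3 = 194 µg.
- Modified MRSD: 194 × 0.74 = 143.6 µg, printed as 143.

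**Step 2. Find the basis of each fraction.**
- 143 / 50 = 2.86, which fits 1/3. The uncut MRSD does not fit: 194 / 50 = 3.88.
- 583 / 50 = 11.7, which fits 1/12.
- 583 / 100 = 5.8, which fits 1/6.

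So the MRSD fraction uses the reduced figure and the NOEL fractions use the unreduced one. Each division is right for its own basis.

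**Step 3. Put the NOEL on the reduced basis.** Weeks 1 to 4 are not reported, so three cases are shown.

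| Assumed shortfall | NOEL (µg/knee) | NOEL / 50 | NOEL / 100 | NOEL / 400 |
|---|---|---|---|---|
| None (as printed) | 583.3 | 11.7 | 5.8 | 1.46 |
| 26% in one of five equal weekly doses | 583.3 × 4.74 / 5 = 553.0 | 11.1 | 5.5 | 1.38 |
| 26% in every week (upper bound) | 583.3 × 0.74 = 431.7 | 8.6 | 4.3 | 1.08 |

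**Step 4. Ask what depends on the choice.** The starting doses do not: 143 / 50 = 2.86 and 143 / 100 = 1.43, so both are below the MRSD after the cut. In the documents, 583 µg is used to derive the MRSD and to describe the starting doses. It does not appear in 3.1, 3.2 or SAP 3.1. The last column of the table therefore measures distance to a ceiling that the plan does not set.

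**Step 5. Set the clauses side by side.**

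| Place | Route A: observed safety and tolerability | Route B: PK data within an exposure limit |
|---|---|---|
| Summary, Protocol 3.1, SAP 3.1 | Yes, no exposure limit attached | Yes, limit not numbered |
| Protocol 3.2 | Yes, no exposure limit attached | Not mentioned |

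Route A reads alike everywhere. Because the routes are alternatives, the exposure limit qualifies only Route B. Section 3.2 leaves out Route B but says nothing against it. Section 3.2 also leaves escalation to the sponsor on a DSMB recommendation. I read a higher added group as another escalation step under that arrangement.

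**Step 6. Plasma against knee.** The dog intra-articular NOEL is 100 / 35 = 2.86 times the efficacious dose. If exposure is dose-proportional (an assumption), plasma AUC at that NOEL would still be 453 / 2.86 = about 159-fold below the IV reference. Plasma alone would indeed be a weak guard for the joint. But the clause does not rest on plasma alone. Route A is human safety and tolerability, which would include events in the knee. Route B cites the nonclinical safety profile as well as toxicokinetics, and that programme included intra-articular studies (Protocol 1.2.2).

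**The case for a change.** The best case for a change is this. The sponsor thought the shortfall serious enough to cut the MRSD, so leaving its parent figure uncut is inconsistent. A dose between about 432 and 583 µg would be below the NOEL on one reading and above it on the other. Added cohorts are a real possibility, since finding the maximum tolerated dose is a secondary objective. The review data listed in Protocol 3.2 and SAP 4.1 do not mention pharmacokinetics, so nobody is named to apply the exposure limit. The dog IV level of 1.25 mg/kg is called a NOEL in 1.2.1 and a NOAEL in 1.2.2, so even the systemic reference is loosely labelled. Clearer wording would cost a few sentences.

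Some of this stands. The bases do differ without a label, the exposure limit is not tied to a figure, and the NOEL/NOAEL wording is uneven. The rest carries less weight. The 432 µg figure needs the maximum shortfall in all five weeks, which the protocol does not report, and a NOEL is not a toxicity threshold. The list of review data is not exclusive. The source of the limit is named as the nonclinical toxicology studies. Protocol 1.2.1 gives rat IV exposures (AUC 2915 ng·h/mL, Cmax 5930 ng/mL) and dog margins, and 1.2.1 and 1.2.2 refer to the Investigator's Brochure. Section 9.7 adds a DSMB charter. Neither of those two documents is available here, so it cannot be said that the limit is undefined for the people who would use it.

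**Conclusion.** No change follows. The printed figures of 583, 194 and 143 µg and the fractions 1/3, 1/12 and 1/6 all reproduce. Putting the NOEL on the same basis as the modified MRSD would move 1/12 to at most about 1/8.6, and 1/6 to at most about 1/4.3. Those limits assume the full 26% shortfall in every week of the dog study. Even then, both starting doses stay below the MRSD.

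The difference between 3.1 and 3.2 is an omitted alternative, not a conflict. The ratios of 1.46 to 1.08 at 400 µg refer to a ceiling that no section adopts, so they do not show a defect in the added-dose clause. What is left is descriptive: unlabelled bases in 1.3.2 and an exposure limit without a cross-reference. Filling those gaps would make the text easier to read but would leave the planned cohorts, pause criteria, analyses and conclusions as they are. This takes no view on which dose or limit is right. It rests on reading the two routes as true alternatives and on 583 µg serving only to derive the MRSD and describe the starting doses.
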